8.4 SUMMARY OF ADVERSE EVENTS FOR SUBJECTS OF SPECIAL INVESTIGATION

The following types of AEs for each subject of special investigation will be summarized with the number of subjects and proportion of the number of subjects with AE and exact 95% confidence intervals. The details of AEs for each subject of special investigation will also be presented in a listing.

CONFIDENTIAL

STATISTICAL ANALYSIS PLAN

- AE
- ADR
- SAE
- SADR
- UAE
- UADR
- Non-serious adverse drug reaction
- AESI
- Adverse events leading to discontinuation

8.5 SUMMARY OF ADVERSE EVENTS FOR SUBJECTS NOT TREATED ACCORDING TO THE APPROVED LABEL

The following types of AEs for each subject who is treated with Esgliteo beyond the scope of approved label will be summarized with the number of subjects and proportion of the number of subjects with AE and exact 95% confidence intervals. The details of AEs for the subjects will also be presented in a listing.

- AE
- ADR
- SAE
- SADR
- UAE
- UADR
- Non-serious adverse drug reaction
- AESI
- Adverse events leading to discontinuation

8.6 SUMMARY OF ADVERSE EVENTS FOR LONG-TERM SAFETY SET

The following types of AEs for Long-term safety set will be summarized with the number of

CONFIDENTIAL

SD 0400 A v4.0
Statistical Analysis Plan
Protocol No.: 1275-0028

26/38 page

Effective Date: 10-Jan-2022

STATISTICAL ANALYSIS PLAN

subjects and proportion of the number of subjects with AE and exact 95% confidence intervals.

- AE
- ADR
- SAE
- SADR
- UAE
- UADR
- Non-serious adverse drug reaction
- AESI
- Adverse events leading to discontinuation

8.7 ANALYSES OF ADVERSE EVENTS FOR LONG-TERM SAFETY SET

The following types of AEs for Long-term safety set will be coded with MedDRA latest major version and will be summarized with SOC and PT using the number of subjects and proportion of the number of subjects with AE. The details of SAEs will also be presented in a listing.

- AE/ADR
- SAE/SADR
- UAE/UADR
- Non-serious adverse drug reaction
- AESI
- Adverse events leading to discontinuation

9. EFFICACY ANALYSIS

Efficacy analyses will be performed on Effectiveness set.

CONFIDENTIAL

STATISTICAL ANALYSIS PLAN

9.1 PRIMARY ENDPOINT

For HbA1c, the changes from baseline to 12 and 24 weeks will be summarized using number of subjects, mean, SD, median, minimum, maximum, 5th percentile and 95th percentile, and will be compared using paired t-test.

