9.3.2.2 Endpoints of effectiveness

9.3.2.2.1 Primary endpoints

- Change from baseline in HbA1c after 12 weeks and/or 24 weeks of treatment

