9.7.3 Analysis of Effectiveness

- ① Mean, standard deviation, minimum value, maximum value, and median of changes in glycosylated hemoglobin(HbA1c) and fasting plasma glucose(FPG), weight, and blood pressure, which were measured at the last visit versus baseline, should be presented, and if there is a difference before administration versus after administration should be analyzed using paired t-test.
- ② If there is difference in the change of glycosylated hemoglobin (HbA1c) according to demographic parameters mentioned in 9.7.1 should be analyzed using t-test or ANOVA (Analysis of Variance).
- ③ The frequency and percentage of patients who had glycosylated hemoglobin(HbA1c) reaching less than 7% (target effectiveness response rate) at the last visit should be calculated, and the frequency and percentage of patients with glycosylated hemoglobin(HbA1c) decreased by at least 0.5% at the last visit should be calculated.
- ④ For final effectiveness evaluation (improved, unchanged, aggravated, unassessable) and 'effective(improved)'/‘ineffective(unchanged, aggravated)’, the number and

percentage of subjects should be mentioned. The final effectiveness evaluation of “Improved” will be classified as “Effective”, “Unchanged” and “Aggravated” will be classified as “Ineffective”. The effectiveness rate and its 95% confidence intervals will be estimated with exact method.

- ⑤ To estimate any factors that are thought to influence an effective ratio, logistic regression analysis should be conducted, and for statistically significant parameters, the meaning should be described.

9.7.4 **Interim Analyses**

In accordance with local regulation for NIS, interim analyses are planned biannually for the initial two years and annually thereafter.

9.7.5 **Handling of Missing Data**

Maximum attempt will be made to ensure the completeness of data collection. All available data will be used in the data analysis.

9.8 **QUALITY CONTROL**

All entries in the eCRF and the existing codings will be stored in a database. The structure of the database is based on the division into sections and entry fields defined in the eCRF. To improve and ensure data quality, data checks will be performed automatically in the eCRF directly on electronic entry at the study site.

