6. DATA HANDLING CONVENTIONS

6.1 HANDLING OF MISSING DATA

All endpoints will be analyzed for OC (observed case) method. In other words, missing data is not replaced.

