9.2 SECONDARY ENDPOINTS

- 1) The frequency, percentage and 95% confidence interval of the changes from baseline to 12 and 24 weeks will be summarized for patients who had HbA1c reaching less than 7% (target effectiveness response rate).
- 2) The frequency, percentage and 95% confidence interval of the changes from baseline to 12 and 24 weeks will be summarized for patients whose HbA1c was decreased by at least 0.5% at the last visit (relative effectiveness response rate).
- 3) For FPG, Weight, SBP and DBP, the changes from baseline to 12 and 24 weeks will be summarized using number of subjects, mean, SD, median, minimum, maximum, 5th percentile and 95th percentile, and will be compared using paired t-test.
- 4) Mean difference in the change of HbA1c from baseline to latest value according to following variables will be analyzed using t-test or ANOVA (Analysis of Variance).
 - Age group (Less than 19 years, 19 years or older and less than 30 years, 30 years or older and less than 40 years, 40 years or older and less than 50 years, 50 years or older and less than 60 years, 60 years or older)
 - Gender (Male, Female)
 - Height (<median, \geq median)
 - Weight (<median, \geq median)
 - Smoking status (Never smoked, Ex-smoked, Currently smokes)
 - Duration of disease (<median, \geq median)
 - Family history of T2DM (Yes, No)
 - Previous allergy (Yes, No)
 - Diabetes mellitus complications (Retinopathy, Neuropathy, Nephropathy, Vasculopathy, Other) (Yes, No, Not applicable)
 - Medical history (Yes, No)

CONFIDENTIAL

STATISTICAL ANALYSIS PLAN

- Comorbidities (Yes, No)
- Prior medication (Yes, No)
- Concomitant medication (Yes, No)
- Other anti-diabetic agent (Yes, No)
- Geriatric population (65 years or more, Less than 65 years)
- Pregnant women (Yes, No, Not applicable)
- Renal impairment (Yes, No)
- Hepatic impairment (Yes, No)
- Long-term use (24 weeks or more)
- Total period of drug use (<median, \geq median)
- Total number of administration (<median, \geq median)
- Average number of administration per day (<median, \geq median)
- Reasons for early interruption (Change to other antidiabetics, Consent withdrawal, Adverse events, Patient refusal to continue taking study medication, Follow up loss, Others)

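### The SAP omits, without declaring it, the overall last-visit effectiveness analysis in protocol 9.7.3; its 12- and 24-week rows leave out some early leavers, and its latest-value subgroup tests have no overall counterpart

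*SAP*

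**What the plan says.** **Protocol, endpoints.** Section 9.3.2.2.1 defines the primary effectiveness endpoint as "Change from baseline in HbA1c after 12 weeks and/or 24 weeks of treatment". The secondary endpoints in 9.3.2.2.2 use the same two time points.

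**Protocol, analysis.** Section 9.7.3 item 1 takes HbA1c, FPG, "weight, and blood pressure, which were measured at the last visit versus baseline, should be presented", with a paired t-test. Item 3 asks for the number and percentage of patients with HbA1c "reaching less than 7% (target effectiveness response rate) at the last visit should be calculated", and for the matching last-visit rate of a fall of at least 0.5%. Section 9.7.5 says that all available data will be used.

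**SAP, overall analysis.** Section 9.1 says of HbA1c that "the changes from baseline to 12 and 24 weeks will be summarized", with a paired t-test. Items 9.2(1) and 9.2(3) use the same two time points for the below-7% rate and for FPG, weight and blood pressure. Section 6.1 sets an observed-case approach in which "missing data is not replaced". Table 4 assigns days 84 to 167 to Visit 2 and day 168 onward to Visit 3, with nothing between baseline and day 84.

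**SAP, where the last visit survives.** Item 9.2(2) summarises weeks 12 and 24 for patients "whose HbA1c was decreased by at least 0.5% at the last visit"; item 9.7(2) does the same for the long-term set. Item 9.2(4) plans "Mean difference in the change of HbA1c from baseline to latest value according to following variables". The final effectiveness evaluation in 9.3 is also taken at the last visit.

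**SAP, declared changes.** Section 11 lists one: average daily dose is replaced by average number of administrations per day.

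**The concern.** An analysis that the protocol specifies has no overall counterpart in the SAP, and the section meant for such departures is silent. Three things follow.

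- The rows planned for HbA1c, FPG, weight, blood pressure and the below-7% rate do not include every patient who has a post-baseline value. The last-visit row would.
- Table D5 (HbA1c change by subgroup, latest value) need not agree in number or mean with either row of Table D1. A reader cannot reconcile the two.
- Items 9.2(2) and 9.7(2) can be programmed in more than one way. Read literally, they describe weeks 12 and 24 only among patients who responded at their last visit. Read loosely, they are response rates at each visit.

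At stake is whether the final report contains the effectiveness summary the protocol promised, and whether patients who stopped early count in an overall estimate.

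**Working it through.** The documents contain no figure to reproduce. The 600 patients are a regulatory requirement, and no expected HbA1c change, SD or early-stop rate is given. The check is therefore a comparison of texts, then an illustration on assumed values.

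**Step 1. Protocol 9.7.3 against the SAP.**

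| Measure | Protocol 9.7.3 | SAP, overall | Last visit kept overall? |
|---|---|---|---|
| HbA1c change | last visit | weeks 12 and 24 (9.1) | no |
| FPG, weight, BP change | last visit | weeks 12 and 24 (9.2(3)) | no |
| HbA1c below 7% | last visit | weeks 12 and 24 (9.2(1)) | no |
| HbA1c fall of at least 0.5% | last visit | mixed (9.2(2), Table D3) | unclear |
| Final evaluation | overall rating | last visit (9.3) | yes |

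The SAP was written against protocol version 4.0. The current protocol's amendment log shows no later change to 9.7.3, so the version gap does not explain the difference.

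**Step 2. Who falls where under Table 4.** Day = visit date - baseline date + 1. Days 29, 57, 78 and 83 fall in no window; days 84, 85, 120 and 167 are Visit 2; days 168, 169 and 200 are Visit 3. So:

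- last seen before day 84: in neither row;
- last seen on days 84 to 167: in the 12-week row, missing from the 24-week row;
- seen on day 168 or later: in the 24-week row. SAP 6.4 takes the latest of several Visit 3 results, so for these patients the 24-week value and the last value coincide.

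Any gap between a 24-week mean and a last-visit mean therefore comes from the first two groups.

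**Step 3. Illustration.** All inputs except N = 600 are assumed. Let *a* be the share last seen before day 84 and *b* the share last seen on days 84 to 167. Completers change by -0.9 at both time points. Leavers change by *m*. Every patient is taken to have a usable post-baseline value.

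- Last visit = (a + b) × m + (1 - a - b) × (-0.9)
- Week 12 = [b × m + (1 - a - b) × (-0.9)] / (1 - a)
- Week 24 = -0.9

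| a, b | n: last / wk 12 / wk 24 | m | Last visit | Week 12 | Wk 24 minus last |
|---|---|---|---|---|---|
| 2%, 5% | 600 / 588 / 558 | 0.0 | -0.837 | -0.854 | -0.063 |
| | | -0.3 | -0.858 | -0.869 | -0.042 |
| | | -0.6 | -0.879 | -0.885 | -0.021 |
| 5%, 10% | 600 / 570 / 510 | 0.0 | -0.765 | -0.805 | -0.135 |
| | | -0.3 | -0.810 | -0.837 | -0.090 |
| | | -0.6 | -0.855 | -0.868 | -0.045 |
| 10%, 15% | 600 / 540 / 450 | 0.0 | -0.675 | -0.750 | -0.225 |
| | | -0.3 | -0.750 | -0.800 | -0.150 |
| | | -0.6 | -0.825 | -0.850 | -0.075 |

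The gap reduces to (a + b) × (m + 0.9) in size: 0.07 × 0.3 = 0.021 at the low end and 0.25 × 0.9 = 0.225 at the high end. The 12-week row differs from the last-visit mean by only 0.006 to 0.075.

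**The case against.** The strongest reply is that the SAP follows the protocol's own endpoint. That is correct: weeks 12 and 24 come from 9.3.2.2, and the protocol is split between its endpoint section and its analysis section. The 12- and 24-week rows are right and should stay. What the reply does not supply is the 9.7.3 analysis beside them, or a declaration that it was left out.

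A reader might also infer several stronger things that the documents do not support.

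- *That last-visit analysis has been abandoned.* It survives in 9.2(4), in 9.3 and, in mixed form, in 9.2(2).
- *That early leavers vanish from the HbA1c results.* Only those last seen before day 84 miss both rows. Item 9.2(4) even tabulates latest-value change by reason for early interruption, and an overall mean could be recovered by weighting the rows of a complete subgroup factor. That recovery covers HbA1c change only, not FPG, weight, blood pressure or the below-7% rate, and no paired test is planned for it.
- *That the protocol's analysis would certainly keep early leavers.* Protocol 9.3.1.4 requires attendance on schedule and excludes patients with missing effectiveness data at visit 2, visit 3, without saying whether one or both. If either visit is enough to exclude, the set is close to completers and the last-visit and 24-week results largely coincide. SAP 4.3 names no visit in its missing-data exclusion.
- *That the planned figures favour the drug.* The listed reasons for stopping include consent withdrawal and loss to follow-up, which have no stated direction.

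It can be added that Table 3 defines the 0.5% response in a way that works at any visit, so 9.2(2) is a wording fault rather than a design fault. It still needs repair, because Table D3 and the text point different ways. Effectiveness is a secondary objective in a single-arm, descriptive study, which limits the stakes.

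**Conclusion.** The point holds as an undeclared omission. Apart from the mixed 0.5% responder item, the SAP has no overall last-visit row for what protocol 9.7.3 items 1 and 3 specify, and Section 11 does not say so. The 12- and 24-week summaries are not themselves an error. Within the main effectiveness set, the latest-value subgroup table has no overall figure to match. In the long-term set, 9.7(4) states no time point, but members are followed for at least 24 weeks, so the 24-week row probably serves there; the wording fault in 9.7(2) remains.

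Neither size nor direction can be derived from the documents. If leavers respond less well than completers, the 24-week mean overstates the HbA1c reduction by about 0.02 to 0.23 points. This range rests on assumed early-stop rates of 7% to 25%, an assumed change of -0.9 in completers and 0.0 to -0.6 in leavers, and a usable post-baseline value for every leaver. It shrinks towards zero if the effectiveness set already excludes most leavers. The correction is worth making because it restores a stated analysis at almost no cost.

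**What to change.** - Keep the 12- and 24-week rows. Add an overall last-visit row (last post-baseline value) to Tables D1 to D4 for all patients in the effectiveness set, with the paired t-test for HbA1c, FPG, weight and blood pressure.
- Reword 9.2(2) and 9.7(2) as the proportion with an HbA1c decrease of at least 0.5% at week 12, at week 24 and at the last visit, and align the titles of D3 and D13.
- List any remaining difference from protocol 9.7.3 in SAP Section 11.

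The cost is one extra row per table and some SAP wording. No new data are needed, and 9.2(4) already requires the latest HbA1c to be derived. The last-visit figure may turn out slightly less favourable than the 24-week one.

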9.2 SECONDARY ENDPOINTS

- 1) The frequency, percentage and 95% confidence interval of the changes from baseline to 12 and 24 weeks will be summarized for patients who had HbA1c reaching less than 7% (target effectiveness response rate).
- 2) The frequency, percentage and 95% confidence interval of the changes from baseline to 12 and 24 weeks will be summarized for patients whose HbA1c was decreased by at least 0.5% at the last visit (relative effectiveness response rate).
- 3) For FPG, Weight, SBP and DBP, the changes from baseline to 12 and 24 weeks will be summarized using number of subjects, mean, SD, median, minimum, maximum, 5th percentile and 95th percentile, and will be compared using paired t-test.
- 4) Mean difference in the change of HbA1c from baseline to latest value according to following variables will be analyzed using t-test or ANOVA (Analysis of Variance).
 - Age group (Less than 19 years, 19 years or older and less than 30 years, 30 years or older and less than 40 years, 40 years or older and less than 50 years, 50 years or older and less than 60 years, 60 years or older)
 - Gender (Male, Female)
 - Height (<median, \geq median)
 - Weight (<median, \geq median)
 - Smoking status (Never smoked, Ex-smoked, Currently smokes)
 - Duration of disease (<median, \geq median)
 - Family history of T2DM (Yes, No)
 - Previous allergy (Yes, No)
 - Diabetes mellitus complications (Retinopathy, Neuropathy, Nephropathy, Vasculopathy, Other) (Yes, No, Not applicable)
 - Medical history (Yes, No)

CONFIDENTIAL

STATISTICAL ANALYSIS PLAN

- Comorbidities (Yes, No)
- Prior medication (Yes, No)
- Concomitant medication (Yes, No)
- Other anti-diabetic agent (Yes, No)
- Geriatric population (65 years or more, Less than 65 years)
- Pregnant women (Yes, No, Not applicable)
- Renal impairment (Yes, No)
- Hepatic impairment (Yes, No)
- Long-term use (24 weeks or more)
- Total period of drug use (<median, \geq median)
- Total number of administration (<median, \geq median)
- Average number of administration per day (<median, \geq median)
- Reasons for early interruption (Change to other antidiabetics, Consent withdrawal, Adverse events, Patient refusal to continue taking study medication, Follow up loss, Others)

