9.2.3.2 Visit 1; Baseline Visit

Upon patient enrolment, the following will be recorded on the patient's eCRF.

- Visit date
- Diagnosis: date of the diagnosis of T2DM, Family history of T2DM
- Inclusion / Exclusion criteria
- Data release consent form: Date of data release consent form

Boehringer-Ingelheim**Non-interventional Study Protocol****BI Study Number 1275-0028****c37168579-01**

Proprietary confidential information © 2022 Boehringer Ingelheim International GmbH or one or more of its affiliated companies

- Demographic data: Year of birth(age), Gender, Pregnancy, Previous allergy, Height, Smoking status
- Diabetes mellitus related complication(Retinopathy, Neuropathy, Nephropathy, Vasculopathy, Others)
- Medical history: Renal impairment, Hepatic impairment, Others. (history of concomitant disease within 6 months prior to baseline)
- Physical examination: Body weight, Blood pressure (SBP, DBP)
- Renal function test: Serum creatinine, eGFR, Urine ACR if blood test result is available(the most recent data prior to baseline)
- Effectiveness assessment: HbA1c, FPG (within 1 month prior to baseline)
- Concomitant anti-hyperglycemic agent: record any anti-hyperglycemic agents that have been taken at least once (within 1 month prior to baseline)
- Concomitant medications: record all medications that have been taken at least once (within 1 month prior to baseline)
- Dose of Esgliteo given (Daily dose, Start date)

At visit 1, the patient will be requested to contact the treating physician in the event of any adverse events noted after initiating Esgliteo treatment.

9.2.3.3 Visit 2; 12 weeks from Visit 1

After 12 weeks from Visit 1, the patients will return for follow-up. The followings will be noted and recorded in the eCRF.

- Visit date
- Physical examination: Body weight, Blood pressure (SBP, DBP)
- Any changes of Esgliteo given
- Effectiveness assessment: HbA1c, FPG (Within 1month prior to Visit 2)
- Renal function test: Serum creatinine, eGFR, Urine ACR if blood test result is available (The most recent data since last visit, except previously entered data)
- Concomitant anti-hyperglycemic agent including new medications taken since last visit: any changes in the concomitant medications (dose and dosing intervals)
- Concomitant medications including new medications taken since last visit: any changes in the concomitant medications (dose and dosing intervals)

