9.4 UNIVARIATE ANALYSIS

The following categorical variables will be summarized using number of subjects, number of efficacy, efficacy rate and 95% confidence interval. Efficacy will be analyzed using Pearson's chi-square test or Fisher's exact test to determine if statistically significant differences exist. (However, if [Diabetes mellitus complications] responds with [Not applicable], [Pregnancy]

CONFIDENTIAL

STATISTICAL ANALYSIS PLAN

responds with [Not applicable], [Height] responds with [Not done], it is excluded from Pearson's chi-square test or Fisher's exact test.)

- Gender (Male, Female)
- Smoking status (Never smoked, Ex-smoked, Currently smokes)
- Family history of T2DM (Yes, No)
- Previous allergy (Yes, No)
- Diabetes mellitus complications (Retinopathy, Neuropathy, Nephropathy, Vasculopathy, Other) (Yes, No, Not applicable)
- Medical history (Yes, No)
- Comorbidities (Yes, No)
- Prior medication (Yes, No)
- Concomitant medication (Yes, No)
- Other anti-diabetic agent (Yes, No)

The following continuous variables will be summarized using number of subjects. Efficacy will be summarized using odds ratio and 95% confidence interval by using simple logistic regression.

- Age (years)
- Height (cm)
- Weight (kg)
- Duration of disease (years)
- Total period of drug use (days)
- Total number of administrations
- Average number of administration per day

Subjects of special investigation will be summarized using number of subjects, number of efficacy, efficacy rate and 95% confidence interval. Efficacy will be analyzed by using Pearson's chi-square test or Fisher's exact test to determine if statistically significant differences

CONFIDENTIAL

STATISTICAL ANALYSIS PLAN

exist.

- Geriatric population (65 years or more, Less than 65 years)
- Pregnant women (Yes, No, Not applicable)
- Renal impairment (Yes, No)
- Hepatic impairment (Yes, No)
- Long-term use (24 weeks or more)

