9.7 SECONDARY ENDPOINTS FOR LONG-TERM EFFECTIVENESS SET

- 1) The frequency, percentage and 95% confidence interval of the changes from baseline to 12 and 24 weeks will be summarized for Long-term effectiveness set who had HbA1c reaching less than 7% (target effectiveness response rate).
- 2) The frequency, percentage and 95% confidence interval of the changes from baseline to 12 and 24 weeks will be summarized for Long-term effectiveness set whose HbA1c was decreased by at least 0.5% at the last visit (relative effectiveness response rate).
- 3) For FPG, Weight, SBP and DBP, the changes from baseline to 12 and 24 weeks will be summarized for Long-term effectiveness set using number of subjects, mean, SD, median, minimum, maximum, 5th percentile, 95th percentile, and will be compared using paired t-test.

CONFIDENTIAL

STATISTICAL ANALYSIS PLAN

4) Mean difference in the change of HbA1c according to following variables will be analyzed for Long-term effectiveness set using t-test or ANOVA (Analysis of Variance).

- Age group (Less than 19 years, 19 years or older and less than 30 years, 30 years or older and less than 40 years, 40 years or older and less than 50 years, 50 years or older and less than 60 years, 60 years or older)
- Gender (Male, Female)
- Height (<median, \geq median)
- Weight (<median, \geq median)
- Smoking status (Never smoked, Ex-smoked, Currently smokes)
- Duration of disease (<median, \geq median)
- Family history of T2DM (Yes, No)
- Previous allergy (Yes, No)
- Diabetes mellitus complications (Retinopathy, Neuropathy, Nephropathy, Vasculopathy, Other) (Yes, No, Not applicable)
- Medical history (Yes, No)
- Comorbidities (Yes, No)
- Prior medication (Yes, No)
- Concomitant medication (Yes, No)
- Other anti-diabetic agent (Yes, No)
- Geriatric population (65 years or more, Less than 65 years)
- Pregnant women (Yes, No, Not applicable)
- Renal impairment (Yes, No)
- Hepatic impairment (Yes, No)
- Total period of drug use (<median, \geq median)
- Total number of administration (<median, \geq median)
- Average number of administration per day (<median, \geq median)

CONFIDENTIAL

STATISTICAL ANALYSIS PLAN

- Reasons for early interruption (Change to other antidiabetics, Consent withdrawal, Adverse events, Patient refusal to continue taking study medication, Follow up loss, Others)

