10.5 DETAILS OF SERIOUS UNEXPECTED AEs

The details of Serious Unexpected AEs collected from use result surveillance, special study (Pharmacoepidemiology study, etc.), clinical trials and Spontaneous reporting will be presented in a listing.

11. Changes to the planned analysis method

In the 9.7.1 demographic analysis item of Protocol (version 4.0), it is described that the administration status of this drug (average daily dose) is analyzed, but since Esglito is a composite, the average number of administrations per day will be analyzed.

[figure not shown]
12. SAS program code

The following SAS program codes will be used.

Table 6 SAS program code

Analysis method	SAS program code
Pearson's chi-square test or	PROC FREQ DATA=dataset;
Fisher's exact test	TABLE ae*factor/CHISQ EXACT; RUN;
Paired t-test	PROC UNIVARIATE DATA=dataset; VAR diff;

CONFIDENTIAL

STATISTICAL ANALYSIS PLAN

Analysis method	SAS program code
	RUN;
t-test	PROC TTEST DATA=dataset; CLASS factor; VAR chg; RUN;
ANOVA	PROC MIXED DATA=dataset; CLASS treatment; MODEL variable=treatment; LSMEANS treatment / PDIFF CL; RUN;
Simple logistic regression	PROC LOGISTIC DATA=dataset; CLASS factor; MODEL ae=factor; RUN;
Multiple logistic regression	PROC LOGISTIC DATA=dataset; CLASS factor1 factor2 factor3; MODEL ae= factor1 factor2 factor3 factor4; RUN;

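### HbA1c change is compared across patient factors with no adjustment for, or display of, baseline HbA1c, so differences in starting level may be read as differences in effectiveness

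*SAP*

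**What the plan says.** Protocol 9.7.3 item 2 asks whether HbA1c change differs "according to demographic parameters mentioned in 9.7.1 should be analyzed using t-test or ANOVA". SAP 9.2 item 4 carries this out on the effectiveness set: "Mean difference in the change of HbA1c from baseline to latest value according to following variables will be analyzed using t-test or ANOVA". Its list has 23 entries, from age group to "Reasons for early interruption (Change to other antidiabetics, Consent withdrawal, Adverse events, Patient refusal to continue taking study medication, Follow up loss, Others". SAP 9.7 item 4 repeats the analysis: "Mean difference in the change of HbA1c according to following variables will be analyzed for Long-term effectiveness set using t-test or ANOVA". That list has 22 entries, because long-term use is dropped.

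Baseline HbA1c is in neither list. The code in SAP Section 12 (Table 6) leaves no room for implicit adjustment. The t-test is "PROC TTEST DATA=dataset; CLASS factor; VAR chg; RUN" and the ANOVA is "MODEL variable=treatment; LSMEANS treatment / PDIFF CL; RUN", each with one class term and no covariate. Baseline HbA1c is also not among the characteristics to be summarised in SAP 7.3.1 and 7.3.2.

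The value is collected. Protocol 9.2.3.2 lists for Visit 1: "Effectiveness assessment: HbA1c, FPG (within 1 month prior to baseline". SAP 5.2 sets a two-sided 5% level for all tests.

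**The concern.** The study is single-arm, and eligibility sets no HbA1c range, so starting values can vary widely. If patients who start higher fall further, two groups with different starting HbA1c will differ in raw change even when they respond identically at any given level. Disease duration, age and diabetic complications are factors whose groups could plausibly start apart, though the documents do not show that they do.

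The planned output gives a mean difference and a p-value for each factor. Nothing beside it tells the reader whether the groups started level. A significant result for disease duration, for example, could then be taken to mean that the drug works better in one group, when it shows only that this group had more room to fall.

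**Working it through.** **Inputs from the documents.** 23 factors (SAP 9.2 item 4) and 22 (SAP 9.7 item 4); two-sided 5% tests (SAP 5.2); 600 patients, a regulatory figure with no effect size, SD or power behind it (Protocol 9.5). There is therefore no figure of the plan's own to reproduce.

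**Assumptions, none of them in the documents.** The fall depends linearly on the patient's underlying starting level, with a slope of -0.3 to -0.6. The SD of change is 1.0 point. There are 500 evaluable patients in two equal groups. The baseline gap between the groups is 0, 0.2 or 0.5 points. The factor has no true effect.

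**Step 1, induced difference.** Spurious difference = |slope| x gap.

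**Step 2, standard error.** SE = 1.0 x sqrt(1/250 + 1/250) = 0.089.

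**Step 3, chance of p<0.05** (normal approximation):

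| Gap | Slope | Difference | In SEs | Rejection |
|---|---|---|---|---|
| 0 | any | 0 | 0 | 5% |
| 0.2 | -0.3 | 0.06 | 0.67 | about 10% |
| 0.2 | -0.6 | 0.12 | 1.34 | about 27% |
| 0.5 | -0.3 | 0.15 | 1.68 | about 39% |
| 0.5 | -0.6 | 0.30 | 3.35 | about 92% |

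**Step 4, does adding baseline help?** A simulation used 600 patients split about equally, a mean baseline of 8.3%, a between-patient SD of 1.2, a within-patient SD of 0.4 at baseline, follow-up noise SD of 0.8, no true factor effect and 2,000 runs per setting. With a slope of -0.5:

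| Gap | Planned t-test: difference, rejection | With baseline HbA1c: difference, rejection |
|---|---|---|
| 0.2 | -0.10, 20% | 0.01, 5% |
| 0.3 | -0.15, 39% | 0.02, 6% |
| 0.5 | -0.25, 81% | 0.03, 7% |

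Over slopes of -0.3 to -0.7 and the same gaps, the planned test rejected in 12% to 93% of runs and the adjusted model in 4% to 7%.

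**Step 5, regression to the mean alone.** With slope 0 (measurement error only) and gaps of 0.2 to 0.5, the planned test showed a raw difference of about 0.00 and rejected in 4% to 6% of runs, which is its nominal rate. Here the adjusted model is the biased one, by 0.02 to 0.05 points, with 5% to 12% rejection. The arithmetic agrees: the reliability of the baseline value is 1.2²/(1.2² + 0.4²) = 1.44/1.60 = 0.90, and the bias is (1 - 0.90) x gap, which is 0.02 at a gap of 0.2 and 0.05 at 0.5.

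**The case against.** The strongest reply is that this is a descriptive item under the secondary objective, and it follows the test that the protocol prescribes. The abstract calls all analyses descriptive. The instruction to describe the meaning of significant parameters is attached to the logistic regressions, not to this comparison. Protocol 9.9.3 concedes residual confounding. A reader might infer that the plan will report these factors as modifying the drug's effect, but neither document says so. The risk is one of interpretation. What remains is that the protocol asks whether change differs by factor and the SAP attaches 5% tests. Protocol 9.9.3 speaks of unmeasured confounding, and baseline HbA1c is measured.

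A reader might also blame regression to the mean for differences between factors. Step 5 shows that it does not produce them on its own, unless groups are formed on the measured value. It bears on the overall paired change in SAP 9.1.

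Nor does the point extend to SAP 9.4 and 9.5. There, "Efficacy will be summarized using odds ratio and 95% confidence interval by using simple logistic regression", but the outcome is the physician's final evaluation, in which maintaining disease-related factors can count as improved. The calculation above does not transfer to that outcome.

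Other limits stand. The documents do not show that any listed factor is associated with baseline HbA1c. Protocol 9.1.2 covers patients switching from the separate tablets, so entry at a high reading cannot be presumed. Baseline HbA1c may be missing for some patients, since the study pays for no tests. The table shells are a separate document and may show an overall baseline mean, although nothing in the SAP provides for baseline by factor level.

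**Conclusion.** The point holds as a risk of misreading in SAP 9.2 item 4 and 9.7 item 4. Where a factor's groups start at different HbA1c and the fall depends on the starting level, the planned test may flag a difference that reflects the starting level only. The size rests wholly on assumed inputs: about 10-27% rejection for a gap of 0.2 points, about 39-92% for 0.5, and the nominal 5% with no gap. Factors unrelated to baseline HbA1c are not distorted in this way. The primary safety objective is untouched, and the paired HbA1c estimate in SAP 9.1 does not depend on this analysis.

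**What to change.** Keep the planned tables and add the following, labelled exploratory:

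1. Report baseline HbA1c overall and by level of each factor.
2. For factors fixed at baseline, add beside the t-test or ANOVA, in both 9.2 item 4 and 9.7 item 4, a linear model of HbA1c change with the factor and continuous baseline HbA1c. Show unadjusted and adjusted results together.
3. Add a descriptive row of HbA1c change by baseline HbA1c category (for example below 7, 7 to <8, 8 to <9, and 9% or above), with a note that it includes regression to the mean.

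The model should not be applied to long-term use, total period of use, number of administrations (total or per day) or reasons for early interruption. These arise after baseline, and adjustment does not make them interpretable. By the definitions in SAP 7.3.5 and 7.3.6, concomitant medication starts on or after the first dose and other anti-diabetic agents are counted during the study, so these two need the same caution. No change to SAP 9.4 or 9.5 is needed on this ground.

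The cost is one covariate in existing code and a few table columns, with no new data. SAP Section 1 already provides for recording a changed analysis and its reason in the final report. The downside is that, in non-randomised groups with an error-prone baseline, the adjustment can add a small bias (about 0.02-0.05 points under the assumptions above), and it does not remove other confounding. That is why both results should be shown.
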